8. PATIENTS, MATERIAL AND METHODS

Type of study: Phase II/III, controlled, randomized, open clinical trial.

By study groups: two parallel groups' design.

By maneuvering: experimental

By measurements in the population: longitudinal

By temporality: prospective

By the nature of the study: clinical

By purpose: Therapeutic

Study Population

- Patients with obesity class III from the "Obesity Clinic" in preparation for bariatric surgery.
- Study period: December 2016 to October 2018
- Place of study: Mexico City, Mexico
- Time of clinical assessment of each patient: one year

Workplan

- 1) A convenience sampling will be done for patients diagnosed with diabetes or prediabetes according to ADA criteria [12] (Appendix 1), who come to Obesity Clinic in the indicated period and that meet the selection criteria. Since the first assessment, patients are informed that they would become candidate for bariatric surgery (bypass or gastric sleeve, depending on surgeons' criteria) once they achieve a weight reduction of 10%.
- 2) Due patients achieve weight loss needed for the surgical procedure at different times of follow-up (3, 6 or 12 months), clinical, biochemical, and initial and final determinations of inflammatory cytokines and hormones, will be collected until the previous valuation before surgery. Data will be collected even if the patients require treatment with sulfonylureas or insulin (adverse event grade 3).
- 3) Prevalence of comorbidities at baseline and the type and dose of drugs used for treatment will be recorded (Appendix 2. Data Collection Sheet). Treating physicians based on the clinical response of patients, will decide the dose and number of drugs and will record changes in the corresponding data sheet.

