6. Use of drugs for weight control.
7. Untreated or uncontrolled hypothyroidism (defined through TSH higher than 4.2 μ U/ml)
8. Pregnant or lactating mother.
9. Tobacco use (in the last month)
10. Current use of steroids or nonsteroidal anti-inflammatory drugs

Withdrawal criteria

1. Becoming pregnant during the study
2. Tobacco use
3. Use of steroids during the study

Sample size

Weight loss after dapagliflozin treatment has not been previously used as primary outcome in randomized controlled trials (RCT) of patients with prediabetes or diabetes and grade III obesity. Zhang et al. performed a meta-analysis that included seven RCTs evaluating the effect of metformin combined with SGLT2-inhibitors (dapagliflozin 10 mg/day, canagliflozin 300 mg/day, empagliflozin 25 mg/day, or ipragliflozin 300 mg/day) vs. metformin (at doses of 1.5 to 3 g/day) with placebo on HbA1c; fasting plasma glucose; and body weight over 24 weeks, 1 year, and 2 years. The total sample was 2847 patients with a mean BMI of 31.7 ± 4.9 kg/m². After a year of treatment, the placebo-metformin control group showed a reduction in body weight of 1.1 ± 3.39 kg, whereas the SGLT-2 inhibitor-metformin group showed a 3.6 ± 4.22 kg reduction with a mean difference of -2.6 kg (-3.17 to -2.03 kg), $p < 0.0000$. Using these data, we calculated a sample size using a mean difference formula. With a power of 80% (alpha level of 0.05) in a two-sided T-test, the sample size required is 90 patients: 45 patients in the M group and 45 patients in the D/M group. The final sample size required is 108 patients: 54 patients in metformin and 54 patients in the dapagliflozin group, allowing for a 20% dropout rate.

Variable definition

Variable name	Variable Type	Scale	Conceptual definition	Operational definition	Units
INDEPENDENT VARIABLES					

Type of treatment	Qualitative, dichotomic	Nominal	Metformin is a biguanide with effect in cyclic AMP kinase that diminishes insulin resistance. Diabetes treatment guidelines consider it as the first line therapy. Dapagliflozin is an SGLT2 inhibitor that induces glycosuria and has been approved for monotherapy in patients with metformin intolerance and also as a second or third line therapy for diabetes.	Use of metformin 2 grams per day or use of metformin 2 grams per day in combination with 10 mg of dapagliflozin.	0 = metformin, 1 = metformin/dapagliflozin
-------------------	-------------------------	---------	--	--	---

DEMOGRAPHIC VARIABLES

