Interleukine 10 (IL-10)	Quantitative continuous	Ratio	Anti-inflammatory cytokine related to the development of atherosclerosis	Concentration determined using the method ELISA.	pg/ml
Ghrelin	Quantitative continuous	Ratio	Hormone secreted in the gastric fundus that induces appetite.	Concentration determined using the method ELISA.	pg/ml

Glucagon	Quantitative continuous	Ratio	Hormone produced by pancreatic alpha cells that counteracts the effects of insulin.	Concentration determined using the method ELISA.	ng/ml
----------	-------------------------	-------	---	--	-------

Statistical analysis: Quantitative variables were described using measures of central tendency and dispersion according to the data distributions. Qualitative variables were described using frequencies or percentages. The Shapiro-Wilk test was used to establish normality in the distribution of quantitative variables. Because information on the different quantitative variables was available up to different time periods, a mixed model analysis was performed using the restricted maximum likelihood (REML) method, as well as a mixed model considering the fixed effects of assigned treatment, sex, and prediabetes or diabetes status, and the random effects of variability in weight loss over time. Comparisons between groups were analyzed using Sidak's post-hoc test. Pearson's chi-square test or Fisher's exact test were used to evaluate the association between qualitative variables. Statistical significance was defined as a $p < 0.05$. Data analysis was performed using SPSS version 17.0 and STATA version 11.0.

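### The final sample size of 108 does not cover the 20% dropout it claims: a 20% loss leaves about 86 patients, not the 90 required (minor)

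*Combined protocol and SAP*

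**What the plan says.** The Sample size paragraph of section 8 takes one-year weight changes from a meta-analysis of SGLT2 inhibitor plus metformin against metformin plus placebo: "1.1 ± 3.39 kg, whereas the SGLT-2 inhibitor-metformin group showed a 3.6 ± 4.22 kg reduction with a mean difference of -2.6 kg". It then says "Using these data, we calculated a sample size using a mean difference formula".

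The design settings are given as "With a power of 80% (alpha level of 0.05) in a two-sided T-test", and the result is that "the sample size required is 90 patients: 45 patients in the M group and 45 patients in the D/M group". The paragraph ends with a final size of 108: "54 patients in metformin and 54 patients in the dapagliflozin group, allowing for a 20% dropout rate".

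The inflation formula is not written out, and nothing else in the document gives the 20% a different meaning. Two other parts of section 8 affect how much a dropout costs. Workplan item 2 says that data "will be collected until the previous valuation before surgery". The Statistical analysis paragraph says: "Because information on the different quantitative variables was available up to different time periods, a mixed model analysis was performed".

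**The concern.** A dropout rate is ordinarily the share of enrolled patients who are lost. On that meaning, 90 required, 20% lost and 108 enrolled cannot all be true. Multiplying the required number by 1.2 adds 20% of the smaller figure, whereas the loss is taken from the larger one, so the enrolled number ends up too small.

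What is at stake is mainly the accuracy of a statement that will be reported and that any reader can check in one line. There is also a small cost in power if the full 20% is lost. The trial's validity is not in question.

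**Working it through.** **Inputs, all from section 8, Sample size.** Required: 90 (45 per arm). Final: 108 (54 per arm). Dropout: 20%. Arm reductions: 1.1 kg (SD 3.39) and 3.6 kg (SD 4.22). Printed mean difference: 2.6 kg, although the arm means differ by 3.6 − 1.1 = 2.5 kg. Two-sided alpha 0.05, power 80%.

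**Step 1. Reproduce the plan's 108.** 45 × (1 + 0.20) = 54 per arm, and 90 × 1.20 = 108. Dividing by (1 − 0.20) instead gives 90/0.80 = 112.5, so 113. Only multiplication gives the stated figure.

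**Step 2. Apply the 20% loss.** 108 × 0.80 = 86.4 in total; 54 × 0.80 = 43.2 per arm. The shortfall against 90 is about 4 patients.

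**Step 3. Find the loss that 108 does cover.** 1 − 90/108 = 16.7%, which is 9 of 54 in each arm.

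**Step 4. Find the size that would cover 20%.** 45/0.80 = 56.25, so 57 per arm and 114 in total.

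Steps 1 to 4 use only the plan's own 90, 20% and 108. The inputs behind the 45 do not affect them.

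**Step 5. Reproduce the 45, to price the shortfall.** The normal formula is n per arm = (1.960 + 0.842)² × (SD₁² + SD₂²) / Δ². With Δ = 2.5 kg and SD 4.22 kg in both arms this gives 44.73, so 45. Twelve combinations were tried: two differences, three SD choices and two formulas.

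| Difference | SDs (kg) | n per arm, normal | n per arm, noncentral t |
|---|---|---|---|
| 2.5 kg | 4.22 in both | 45 | 46 |
| 2.6 kg | 4.22 in both | 42 | 43 |
| 2.5 kg | 3.39 and 4.22 | 37 | 38 |
| 2.6 kg | 3.39 and 4.22 | 35 | 36 |
| 2.5 kg | 3.39 in both | 29 | 30 |
| 2.6 kg | 3.39 in both | 27 | 28 |

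Only the first, under the normal formula, gives 45.

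**Step 6. Power at 45 and at 43 per arm.** Under the normal formula, power is Φ(Δ / √((SD₁² + SD₂²)/n) − 1.960). For 2.5 kg and SD 4.22 kg in both arms:

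- n = 45: Φ(2.810 − 1.960) = 80.2%
- n = 43: Φ(2.747 − 1.960) = 78.4%

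| Difference, SDs | Normal, 45 to 43 per arm | Noncentral t, 45 to 43 per arm |
|---|---|---|
| 2.5 kg, 4.22 in both | 80.2% to 78.4% | 79.4% to 77.5% |
| 2.6 kg, 4.22 in both | 83.2% to 81.5% | 82.4% to 80.6% |
| 2.5 kg, 3.39 and 4.22 | 87.3% to 85.7% | 86.5% to 84.9% |
| 2.6 kg, 3.39 and 4.22 | 89.7% to 88.3% | 89.0% to 87.6% |

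With SD 3.39 in both arms, power at 43 per arm is above 92% under either formula.

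**The case against.** The strongest reply is that this is a choice of inflation rule rather than a miscalculation. 45 × 1.2 is 54, and adding 20% to the required number is common practice. That is fair as a description of what was done. It does not rescue the sentence, because the text claims to allow for a 20% dropout rate and 108 does not.

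A second reply is that dropout here is not total loss of data. Measurements are kept up to the last assessment before surgery, follow-up continues in patients who need insulin or sulfonylureas, and the mixed model uses partial follow-up. This stands: 86 is the number who complete, and the information lost may be less than that number suggests. The power figures at 43 per arm assume that a dropout contributes nothing.

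A third reply is that the drop below 80% depends on inferred inputs. This also stands. The plan does not say that 2.5 kg and SD 4.22 kg were used; they are inferred because they reproduce 45. The plan names a t-test, and an exact t-test on those inputs needs 46. The match shows that 45 is obtainable from the printed data, so no error in the 45 is alleged, but it does not prove how 45 was reached.

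None of these replies alters the mismatch between 90, 20% and 108.

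**Conclusion.** The concern holds and is minor. The stated 108 withstands a loss of 16.7%, split evenly between arms, and not the 20% claimed; after a 20% loss about 86 patients (43 per arm) remain against 90 required. This rests only on the plan's three figures and on reading dropout as a share of those enrolled.

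The cost in power is 1.8 percentage points (normal formula) or 1.9 (noncentral t) on the inputs that reproduce 45, if dropouts contribute no data. On every other reading tried, power at 43 per arm stays above 80%. The sentence should be corrected because it will be reported and contradicts itself. The size of the effect does not call for more patients.

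**What to change.** Replace the last sentence of the Sample size paragraph with a statement of what 108 delivers, for example:

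> We will randomise 108 patients (54 per arm). This leaves 90 (45 per arm) if no more than 16.7% are lost, evenly between arms, and about 86 (43 per arm) after a 20% loss.

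In the same place, name the difference, SD and formula that gave 45, and state power at 45 and at 43 per arm under that one formula. If the inputs were 2.5 kg and SD 4.22 kg in both arms, those values are 80.2% and 78.4% by the normal approximation, or 79.4% and 77.5% by the noncentral t. Add that the figures at 43 assume dropouts contribute no data.

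The cost is a text change only: enrolment, visits and analysis stay as they are. On the inputs that reproduce 45, the protocol would then openly state power slightly below 80% after a 20% loss. Keeping the 20% claim unchanged would instead require 57 per arm, 6 more patients in total (114 − 108), which the size of the shortfall does not justify.

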The Mexican Social Security Institute (IMSS) has the broader coverage of health of the country. According to ENSANUT 2012, 74.4% of its beneficiaries are obese and it is estimated that only 50% receive medical attention focused on weight control (e.g. diet or physical activity recommendations). Considering the current increase in the prevalence of obesity and an imperious need of reducing the prevalence of co-morbidities and high mortality rate associated with this disease, since 2008 the Hospital de Especialidades from the Centro Medico Nacional Siglo XXI organized a multidisciplinary team composed by members from departments of Endocrinology, Clinical Nutrition, Bariatric Surgery, Psychiatry and Internal Medicine, under the name of "Obesity Clinic".

The requirements for admission are a BMI greater than 35 kg/m² with a major comorbidity (diabetes, hypertension, dyslipidemia or sleep apnea syndrome) or obesity class III. Patients are initially evaluated by nutritionists authorized to assess anthropometric measures, who also adjust diet based on weight and initial consumption of calories and evaluate patients monthly recording weight, waist and hip circumference, percentage of adherence to diet and amount of physical exercise per week (measured in minutes per week). At the same time, the endocrinologists perform clinical assessment and laboratory tests for detection and control of comorbidities such as altered metabolism of glucose (Type 2 diabetes [T2D] or pre-diabetes), hypertension (HTN) and dyslipidemia and request assessment and treatment of other specialists if necessary. Meanwhile, psychiatrists perform tests for detection and treatment of anxiety disorders or depression, eating disorders, personality disorders and other psychiatric comorbidities that could influence negatively on the management of patients and finally, once the patients lost 10% of excess of weight, they become candidates for bariatric surgery (laparoscopic Roux-Y bypass or gastric sleeve, depending on the evaluation of surgeons).

Several studies support that weight reduction before surgery decreases surgical risk and improves time to recovery. It has been observed that patients with super-obesity have a higher incidence of complications during bariatric surgery associated with increased technical difficulties (for example an increased liver volume due to steatosis), increased anesthetic risk and risk of treatment failure.

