- 4) Patients will be randomized by a random numbers system generated with a computational software and will be assigned to a group: 1) metformin (2 g/day) or 2) metformin (2 g/day) and dapagliflozin 10 mg. All patients will receive dietary treatment and follow-up during the study by Nutrition service. Dietary treatment is individualized, as it is based on the initial weight of the patient and their eating habits at the time of valuation. It is expected that dietary treatment does not influence the results because all patients will undergo diet and those with little attachment (defined as failure to comply with at least 80% of the prescribed diet) are discharged of the surgical protocol. The Nutrition service calculates the percentage of adherence to diet.
- 5) Once assigned to the corresponding group, patients will receive an identification code that will be retained throughout the study. One of the researchers not directly involved in patient care, will assign tablets needed for daily intake for a month and then the number of tablets required for 3 months in a sealed envelope.
- 6) A run-in period will be used to assess tolerance to treatments. This period will be for a month. At this time patients will be advised of a possible increase on urea and will be instructed in the relevance of increasing fluid intake.
- 7) The anthropometrical and biochemical variables will be recorded at baseline and at 1, 3, 6 and 12 months (Appendix 2. Data Collection Sheet). A clinical nutritionist accredited as Level 1 Anthropometrist by the International Society for the Advancement of Kinanthropometry (ISAK) will assess the weight on a scale with a

maximum capacity of 300 kg and precision of 100 g; height using an stadiometer, and waist circumference using a fiberglass tape, according to the manual of procedures for nutrition projects of the Centro de Investigación en Nutrición y Salud de Instituto Nacional de Salud Pública [86], and also in accordance with the procedures manual for the assessment of clinical and anthropometrical measurements in the adult and elderly of the Ministry of Health [87] (Appendix 3. Clinical and anthropometric measurements).

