Age	Quantitative, continuous	Ratio	Time elapsed from birth to	Time elapsed from birth to the baseline registry of the patient.	years
-----	--------------------------	-------	----------------------------	--	-------

			the current date.		
Gender	Qualitative, dichotomic	Nominal	Taxon that gathers members of the same species.	Gender assigned in the registry documents.	0 = female 1 = male
Height	Quantitative, continuous	Ratio	Length of a human body when measured in a standing position from the top of head to the floor.	Height registered in the baseline documents using the same stadiometer in all patients during the first evaluation.	meters (m)
Body mass index (BMI)	Quantitative continuous	Ratio	Measurement that associates height and size in the same individual and classifies them as underweight, normal, overweight or obese.	Ratio between weight in kilograms (kg) divided by the square of the height in meters. Calculation is performed in every clinical evaluation during the protocol.	kg/m²
DEPENDENT VARIABLES					
Weight	Quantitative continuous	Ratio	The force that gravitation exerts upon a body.	Total amount of kilograms registered in the same person using the same calibrated scale at baseline and months 3, 6 and 12.	kilograms (kg)

Waist circumference (WC)	Quantitative continuous	Ratio	Measurement of the body circumference measured at the minimum circumference between the iliac crest and the rib cage.	Perimeter registered in the documents using the same flexible tape at baseline and months 3, 6 and 12.	centimeters (cm)
Fasting Glucose	Quantitative continuous	Ratio	Glucose concentration in the blood serum after an 8 hour fast.	Blood glucose reported at baseline, months 3,6 and 12.	mg/dl
Fasting Insulin	Quantitative continuous	Ratio	Insulin concentration in the patients serum determined by radioimmunoassay after an 8 hour fast.	Blood insulin reported at baseline and months 3,6 and 12.	mU/L
HOMA-IR	Quantitative continuous	Ratio	The homeostatic model assessment (HOMA) is a method used to quantify insulin resistance and beta-	HOMA = [glucose (mg/dl)/18 *insulin (mU/L)]/22.5 at baseline and months 3,6 and 12.	Dimensionless

			cell function.		

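### Surgery ends follow-up once enough weight is lost, but the trial schedules few weights and no pre-operative one; if unrecorded monthly weights decide candidacy, the arm difference may be pulled towards zero

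*Combined protocol and SAP*

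**What the plan says.** **Exit.** The Abstract uses the data of patients advised to have surgery until the operation. In Section 8, Workplan item 2, data "will be collected until the previous valuation before surgery". Candidacy depends on weight loss, but the threshold is given in two ways: a 10% weight reduction (Workplan item 1) and 10% of excess weight (Section 7, account of the Obesity Clinic). Item 2 places the reaching of the threshold at 3, 6 or 12 months of follow-up.

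**Trial weights.** Workplan item 7: "The anthropometrical and biochemical variables will be recorded at baseline and at 1, 3, 6 and 12 months (Appendix 2. Data Collection Sheet"). The follow-up table in Appendix 2 has the same four post-baseline columns. The Abstract and the variable table leave out month 1; the latter has "Total amount of kilograms registered in the same person using the same calibrated scale at baseline and months 3, 6 and 12". By contrast, cytokines and hormones are to be sampled before surgery (item 9), and Appendix 2 gives most of them a final column.

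**Clinic weights.** Section 7 says that the nutritionists "evaluate patients monthly recording weight, waist and hip circumference, percentage of adherence to diet". Nothing brings these values into the trial data.

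**Analysis.** The statistical section chooses a REML mixed model because data end at different times. It states no missing-data assumption and no time point for the treatment contrast.

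**The concern.** A likelihood mixed model copes with outcome-driven exit if, given the recorded weights, leaving does not depend on unrecorded ones. No weight is scheduled between months 6 and 12, and none is tied to surgery. Suppose a patient crosses the threshold at an unscheduled monthly weighing and is operated on before the next study visit. The weight that led to exit is then not scheduled to be recorded, and the model extrapolates from earlier, smaller losses. The hypothesis expects greater loss on the combination, so more such exits would fall in that arm and the difference would shrink.

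The responder percentages (Section 6, objective b.iii) are exposed more directly. A patient who passes a cut-off between visits and then leaves would be counted at an earlier, lower loss, and the mixed model does not repair a simple percentage.

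**Working it through.** **1. The plan's own figure.** Inputs from Section 8, Sample size: "the placebo-metformin control group showed a reduction in body weight of 1.1 ± 3.39 kg"; the combination group "showed a 3.6 ± 4.22 kg reduction with a mean difference of -2.6 kg (-3.17 to -2.03 kg"); "With a power of 80% (alpha level of 0.05) in a two-sided T-test, the sample size required is 90 patients", that is "45 patients in the M group and 45 patients in the D/M group". The arm means differ by 3.6 − 1.1 = 2.5 kg. With the larger SD:

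n per arm = 2(1.960 + 0.842)² × 4.22² / 2.5² = 2 × 7.85 × 17.81 / 6.25 = 44.7, so 45. This reproduces the plan. A difference of 2.6 kg would give 42.

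**2. Simulation.** 60,000 patients per arm. A patient leaves when a monthly loss reaches the threshold, and weights are kept only at months 1, 3, 6 and 12. The estimate is the arm difference at month 12. Two analyses were fitted: visits with unstructured covariance, and a random-slope model given the correct time shape.

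From the documents: losses of 1.1 v 3.6 kg with SDs 3.39 and 4.22, and the hypothesis of 5% v 10% (Section 5).

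Assumptions not in the documents:
- Baseline weight 120 kg, so the hypothesis becomes 6 v 12 kg; SD 6 kg in that case.
- Thresholds of 12 kg (10% of weight) and 5.2 kg (10% of excess over BMI 25). The latter means 52 kg of excess, hence 68 kg at BMI 25 and a height of √(68/25) = 1.65 m.
- Within-patient weight SD of 1 or 2 kg; linear or saturating course; 0 to 3 months from threshold to surgery.

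Results if unrecorded monthly weights decide and exit is immediate:

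| True difference | Threshold | Unstructured | Random slope |
|---|---|---|---|
| 2.5 kg | 12 kg | 2.36 to 2.53 kg for both models (−6% to +1%) | as left |
| 2.5 kg | 5.2 kg | 1.22 to 2.04 kg (−51% to −18%) | 1.84 to 2.27 kg (−27% to −9%) |
| 6 kg | 12 kg | 4.91 to 5.76 kg (−18% to −4%) | 5.69 to 5.96 kg (−5% to −1%) |
| 6 kg | 5.2 kg | 3.22 to 4.38 kg (−46% to −27%) | 5.56 to 5.75 kg (−7% to −4%) |

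The threshold matters because it sets how many patients leave. With a linear course and the 2.5 kg difference, 13% v 36% (noise SD 1 kg) or 27% v 52% (SD 2 kg) reach 5.2 kg before month 12, most of them in an unscheduled month. Only 0% v 2 to 3% reach 12 kg.

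A wait before surgery helps, because a study visit may fall within it. With three months, the unstructured loss ranges from 0% to 28%.

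**3. Comparison cases.** If the threshold is judged at recorded months 3 and 6, bias is within about 2% in 14 of 16 scenarios (worst −10%). If monthly weights decide and all of them enter the model, it is again within about 2% in 14 of 16 (worst −13%). Adding only the triggering weight leaves −3% to +7%.

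**4. Power.** At 45 per arm and SD 4.22, power = Φ(Δ√(45/2)/4.22 − 1.96):
- Δ = 2.5: Φ(0.850) = 80%
- Δ = 2.04: Φ(0.333) = 63%
- Δ = 1.84: Φ(0.108) = 54%
- Δ = 1.22: Φ(−0.589) = 28%

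**The case against.** A reader might infer that the triggering weights are discarded and that the 12-month difference is therefore biased. The documents do not support that. Workplan item 2 puts the reaching of the threshold at 3, 6 or 12 months, all recorded visits, and its cut-off is the previous valuation, without saying that this must be a study visit. The Abstract keeps data until surgery. The BMI row of the variable table calculates BMI, which needs a weight, at every clinical evaluation. If candidacy is judged at recorded visits, exit depends on recorded weights and the mixed model is largely protected.

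The model matters too. The plan's random effects for weight loss over time read more naturally as random slopes than as unstructured visits, and the attenuation is then smaller. A halving of the effect appears only with the lower threshold, the noisier weights and the unstructured model.

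All of this stands, and it makes the point conditional. It does not close it. Item 2 does not name the weighing that decides, and Section 7 describes candidacy alongside monthly weighing. Data kept until surgery also need somewhere to be entered, and Appendix 2 has no such place for weight.

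A reader might also count a loss of precision in time to surgical readiness. Section 4 mentions a shorter wait only as a possible benefit, and it is not among the Section 6 objectives.

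**Conclusion.** The gap in recording is documented; the bias is possible but not established. It is near zero in most scenarios if recorded visits decide candidacy. If unrecorded monthly weights decide, the difference may be pulled towards zero. For a true 2.5 kg, that is about 0 to 6% at 10% of total weight; at 10% of excess weight it is about 9 to 27% with random slopes or 18 to 51% with unstructured visits.

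These sizes rest on the assumed baseline weight, noise, weight course and immediate exit. The random-slope figures also assume that the time shape is modelled correctly. Month 12 is the time point used here because the plan names none. The possible understatement of responder percentages follows by reasoning and was not simulated.

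**What to change.** - In Workplan item 7, the variable table and Appendix 2, record as study data every monthly clinic weight and waist up to surgery, including the last pre-operative one, with its actual date and in both arms.
- In the statistical section, enter these values in the mixed model at their actual time, and use them for the responder percentages in objective b.iii.
- State which weighing decides candidacy. Reconcile the two surgery thresholds (Section 7 and Workplan item 1), and the month-1 discrepancy between Workplan item 7 with Appendix 2 and the Abstract with the variable table.
- Leave the laboratory schedule, including month 1, unchanged.

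The cost is transcription, extra columns in Appendix 2 and a sentence or two in the analysis section; no new visit or procedure is needed. The statistical section is written in the past tense, so follow-up may be over; the weights could then still be sought in clinic records. One drawback is that monthly weights may be taken by someone other than the accredited anthropometrist of item 7, so the assessor and scale should be recorded with each value. Some bias may remain: the worst simulated case with all monthly weights was −13%.
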